6.2. Preparation, Handling, Storage, and Accountability

The investigator or designee must confirm appropriate storage conditions have been maintained during transit for all study interventions received and any discrepancies are reported and resolved before use of the study intervention.

Only participants enrolled in the study may receive study intervention. Only authorized study personnel may supply, prepare, or administer study intervention. All study intervention must be stored in a secure, environmentally controlled, and monitored (manual or automated) area in accordance with the labeled storage conditions with access limited to the investigator and authorized study personnel.

The investigator or authorized study personnel are responsible for study intervention accountability, reconciliation, and record maintenance; that is, receipt, reconciliation, and final disposition records.

Further guidance and information for the final disposition of unused study interventions are provided in the Pharmacy manual.

Study intervention will be dispensed at the study visits summarized in the SoA.

6.3. Measures to Minimize Bias: Randomization and Blinding

Randomization

All participants will be centrally assigned through block randomization with a block size of 2 using an IWRS. Before the study is initiated, the login information and directions for the IWRS will be provided to each site.

Participants will be randomly assigned in a 1:1 ratio to tirzepatide or dose escalation of dulaglutide.

Participants will be stratified based on

- starting dulaglutide dose at Screening (0.75 mg, 1.5 mg)
- region (NA, EU)
- number of OAM (0-1 or 2-3), and
- HbA1c ($\leq 8.5\%$ or $> 8.5\%$).

Blinding

This is an open-label study.

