4.1. Overall Design

SURPASS-SWITCH is a Phase 4, randomized, open-label, active-controlled, parallel-group, multicenter, multinational trial to assess the efficacy and safety of tirzepatide 15 mg or MTD compared to dulaglutide 4.5 mg or MTD in participants with T2D.

This study will enroll participants with inadequately controlled T2D who are taking dulaglutide once weekly (0.75 mg or 1.5 mg) for at least 6 months prior to Visit 1, with or without (up to 3) background OAMs.

The maximum duration of study participation is approximately 47 weeks. This study includes

- an approximate 3-week screening period
- a 40-week treatment period, and
- a 4-week safety follow-up period.

See the SoA (Section 1.3) for additional details about the study periods and visit-specific assessments, including assessments needed at an ED visit.

Participants will be randomly assigned 1:1 to either

- continue with and escalate dulaglutide to 4.5 mg or MTD, or
- tirzepatide 15 mg or MTD.

Participants who are randomly assigned to tirzepatide will discontinue dulaglutide and initiate tirzepatide within 3 days of their next scheduled dose. The starting dose for tirzepatide is 2.5 mg once weekly for 4 weeks, escalated in 2.5-mg increments every 4 weeks until 15 mg or MTD is achieved, as described in Section 6.1.1.

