**Method of treatment assignment**

Participants who meet all entry criteria for enrollment will be centrally assigned to 1 of the study treatments arms at Visit 3. Assignment to treatment arms will be determined by a computer-generated random sequence using an interactive web-response system (IWRS).

Participants will be randomly assigned in a 1:1 ratio to tirzepatide or dose escalation of dulaglutide.

Participants will be stratified based on

- starting dulaglutide dose at screening (0.75 mg, 1.5 mg)
- region (North America, European Union)
- number of OAMs (0 to 1 or 2 to 3), and
- HbA1c ( $\leq 8.5\%$  or  $> 8.5\%$ ).

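### A fixed block size of 2, printed in an open-label 1:1 protocol, makes the second assignment of each pair certain to anyone who sees the whole stratum; a single site seeing only its own participants learns little

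*Protocol*

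**What the plan says.** Protocol Section 6.3 gives one block size: "All participants will be centrally assigned through block randomization with a block size of 2 using an IWRS". The ratio follows: "Participants will be randomly assigned in a 1:1 ratio to tirzepatide or dose escalation of dulaglutide". Under Blinding the section says "This is an open-label study".

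The list opened by "Participants will be stratified based on" has four two-level factors: starting dulaglutide dose, region (NA or EU), number of OAMs, and HbA1c at or below versus above 8.5%. Site is not among them, so each stratum runs across all sites of a region.

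The Protocol Amendment History (Section 10.10) shows that amendment (a) added the block size to Section 6.3 deliberately, as a clarification. That amendment's general rationale was regulatory feedback.

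The SAP, under Method of treatment assignment, says "Assignment to treatment arms will be determined by a computer-generated random sequence using an interactive web-response system (IWRS") and repeats the strata without a block size. Neither document mentions varying block sizes, withholding the size from sites, or limiting who may see assignments across sites.

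**The concern.** In an open-label trial, the main protection against selection bias at entry is that nobody involved in enrolment can foresee the next assignment. Two is the smallest block a 1:1 ratio permits, it does not vary, and every protocol holder can read it. Open-label treatment then reveals the first member of each pair, which settles the second.

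There is room for foreknowledge to act. Exclusion criteria 28 and 31 rest on the investigator's opinion, Section 5.4 allows one rescreening at the investigator's discretion, and Section 4.1.1 has criteria confirmed at Visit 3 just before randomization. All participants already take one of the two drugs, so a preference for steering some towards the other is plausible, although the documents contain no evidence of one. At stake is the comparability of the arms on characteristics that the analysis model does not adjust for.

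**Working it through.** **Inputs.** From Protocol 6.3: block size 2, ratio 1:1, four two-level factors, open-label. From Protocol 9.5: about 250 participants. That gives 2^4 = 16 strata, on average 250/16 = 15.6 participants each. The documents give neither site numbers nor stratum sizes (Protocol 4.1: "randomized, open-label, active-controlled, parallel-group, multicenter, multinational trial to assess the efficacy and safety"). Site figures below therefore assume 10 to 50 equal sites, half in each region.

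**The plan's own figures.** The documents give none for predictability. The power statement reproduces: with a difference of 0.58, SD 1.3 and 15% loss, 125 × 0.85 = 106 per arm gives 90.1% power (normal approximation). Block size does not enter this calculation.

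**Observer of a whole stratum, fixed blocks.** For block size B at 1:1, the share of assignments made when only one arm remains in the block is 1/(B/2 + 1). Best-guess accuracy comes from enumerating all blocks. For B = 2 it is (0.5 + 1)/2 = 75%.

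**Randomly varied blocks.** This is a simulation with 16 participants per stratum. The observer sees the whole stratum and knows which sizes are in use, but not their order.

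| Scheme | Certain | Guessed correctly |
|---|---|---|
| Fixed 2 | 50.0% | 75.0% |
| Fixed 4 | 33.3% | 70.8% |
| Fixed 6 | 25.0% | 68.3% |
| Random 4 and 6 | about 5.9% | about 68.4% |

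Under block 2, the certain assignments number 250/2 = 125 if every stratum ends on an even count, and (250 − 16)/2 = 117 if all 16 end on an odd count.

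**Entries consecutive in a stratum.** Guess the opposite of the previous assignment.
- Block 2: (1 + 0.5)/2 = 75%.
- Blocks of 4 and 6, equally likely: (3 × 2/3 + 0.5 + 5 × 3/5 + 0.5)/10 = 6/10 = 60%. The fair comparator is therefore 60%, not 50%.

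**One site seeing only its own participants, block 2.** Let s be the site's share of the stratum. A participant's pair-mate was enrolled earlier at the same site with probability s/2. In those cases, guessing the opposite of the site's last assignment in the stratum is always right; otherwise it is right half the time. Accuracy is 0.5 + s/4.

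| Sites (assumed) | s | Accuracy |
|---|---|---|
| 10 | 0.20 | 55% |
| 20 | 0.10 | 52.5% |
| 35 | 0.057 | 51.4% |
| 50 | 0.04 | 51% |

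A separate simulation (250 participants, an assumed mix of 16 strata, 600 runs) compared the schemes at 10, 20 and 40 sites. Correct guesses were 54.5%, 52.6% and 51.7% under block 2, and 54.0%, 52.4% and 51.6% under blocks of 4 and 6. The gain is at most 0.5 percentage points. A dominant site is different: s = 0.5 gives 62.5%, and s = 1 gives the full 75%.

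**Cost in balance.** The same simulation gives a mean absolute difference between arm totals of 2.2 under block 2 and 3.0 under blocks of 4 and 6. Within a stratum, the largest possible imbalance is 1 under block 2 and 3 with a block of 6.

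**The case against.** The strongest reply is that selection bias needs foreknowledge in the person who decides on entry. That is the site investigator, who sees one site's participants in a stratum shared across a region and usually cannot tell whether the next entry opens or closes a pair. For that person the change is worth at most half a percentage point. Study-team members and monitors do not enrol, and nothing says that they see cumulative assignments by stratum or pass them on. This stands, and it limits the point to a modest one.

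Second, HbA1c is measured centrally, both at entry and as the endpoint, and the model adjusts for baseline HbA1c, dulaglutide dose, region and number of OAMs. That limits bias through those factors but does not replace concealment for anything unmeasured.

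Third, small blocks have a real if modest merit: with about 16 participants per stratum, they keep the arms close within each stratum. That also stands.

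A reader might infer that every site can foresee every second assignment. The documents do not support this, because assignment is central and site is not a stratification factor. It would follow only if the IWRS ran separate lists by site, which is nowhere stated. Nor does the SAP's silence on block size contradict the protocol: the SAP is based on the protocol of 01 July 2022, and the sentence came with amendment (a) of 20 January 2023.

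**Conclusion.** The point holds for anyone who can see a whole stratum: about 50% of assignments certain and 75% guessed correctly, against about 6% and 68% with randomly varied blocks of 4 and 6. The main gain is in certainty; guessing accuracy improves by about 7 points. This part follows from Section 6.3 alone, apart from the 16-per-stratum assumption behind the varied-block figures.

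For an ordinary site the exposure is small, and the change makes almost no difference there. That conclusion depends on the assumed 10 to 50 equal sites. The remaining routes are a cross-site view, a site that supplies most of a small stratum, and entries known to be consecutive in a stratum. The documents restrict none of them, but they do not show that any is open in practice.

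This is an inexpensive improvement to concealment. It is not evidence that the trial's result is biased, and it does not affect sample size or power.

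**What to change.** 1. Replace the block-size sentence in Protocol 6.3; do not simply delete it, since amendment (a) added it on purpose. Suggested text: *stratified permuted blocks of randomly varying size; details are held in a restricted randomization document*.
2. Set the IWRS to randomly varied blocks, for example 4 and 6, within the existing 16 strata.
3. State who may see cross-site assignments by stratum, and restrict that access to those who need it.
4. If enrolment has begun, document who has had such access, and compare baseline characteristics of first and second members of pairs.

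The cost is an IWRS setting and an amended sentence that rewords a recent disclosure. Mean overall arm imbalance rises from about 2 to about 3 of 250, and imbalance within a stratum can reach 3 instead of 1.

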6.4. Study Intervention Compliance

Participants will enter the intervention dose information in their eDiary.

The investigator or trained designee will assess treatment compliance at each visit based on review of the participant's glycemic control, eDiary completion, and adherence to prescribed dose and study procedures.

If a participant is considered poorly compliant with their study procedures, for example, missed visits or specific diagnostic tests, they will be retrained as needed by designated study personnel.

6.5. Dose Modification

For general dose escalation, see Section [6.1.1](#).

Missed doses of study intervention are described in Section [7.1.3](#).

6.5.1. Management of Participants with Gastrointestinal Symptoms

The dose escalation scheme is designed to minimize the development of intolerable GI symptoms.

This table describes steps the investigator should follow to mitigate GI symptoms and manage participants with intolerable GI AEs for both the tirzepatide and dulaglutide treatment groups.

STEP 1	Advise participants to eat smaller meals, for example, splitting 3 daily meals into 4 or more smaller meals, and to stop eating when they feel full.
STEP 2	Continue STEP 1 + Treat with symptomatic medication, for example, anti-emetic or anti-diarrheal medication, per local country availability and individual participant needs. Use of symptomatic medication should be captured as concomitant medication in the CRF.
STEP 3	Continue STEP 1 + STEP 2 + Manage GI symptoms, including considering dose interruption. Temporarily interrupt study intervention; 1 dose can be omitted per 4 weeks. After the interruption, the investigator should restart the dose or escalate the dose as required, with the participant taking medication to alleviate their GI symptoms. The data related to temporary interruption of study treatment should be documented in source documents. Refer to Section 6.5.1 . for additional details.
STEP 4	If intolerable GI symptoms persist despite the above measures, the investigator may decide to reduce the dose to the previous MTD.

Abbreviations: CRF = case report form; GI = gastrointestinal.

6.5.2. Study Intervention Dose Modification

If a participant experiences GI tolerability issues despite the measures listed in Section [6.5.1](#), then follow the guidance in this table.

If a participant is currently taking...	then...
Tirzepatide 2.5 mg or 5 mg, or dulaglutide 0.75 mg	permanently stop study intervention, remain in the study, and initiate another antihyperglycemic medication.
Any other tirzepatide or dulaglutide dose	reduce the dose to the previous tolerated dose. Note: If a participant's dose is reduced, the investigator may re-escalate the dose twice when considered appropriate.

Participants who permanently stop study intervention will receive another locally approved antihyperglycemic medication, if needed, per clinical judgment of the investigator, and will continue participating in the study according to the protocol to collect all planned efficacy and safety measurements per the SoA (Section 1.3), Adverse Events (Section 8.3), and Safety Assessments (Section 8.2) of this protocol.

The choice of antihyperglycemic medication will be at the discretion of the investigator. The investigators should follow current published standards of care from the American Diabetes Association and/or the consensus report by the American Diabetes Association and the European Association for Study of Diabetes (ADA 2022; Buse et al. 2020).

GLP-1 RAs and tirzepatide are not allowed as antihyperglycemic medication.

The new antihyperglycemic medication will be recorded on the CRF for antihyperglycemic medications.

6.6. Continued Access to Study Intervention after the End of the Study

Study intervention will not be provided to participants after completion of the study. At the end of study participation, participants will be treated according to local practice for type 2 diabetes and according to what is available in local markets. Treatment decisions can be made by the participant's primary physician but may also be made by the study investigator.

6.7. Treatment of Overdose

Tirzepatide overdose is defined as administration of tirzepatide with more than the intended dose (more than 1 injection) in less than 72 hours.

Dulaglutide overdose is defined and will be treated, according to the locally approved labeling and packaging.

In the event of an overdose, the investigator or treating physician should

- contact the Lilly medical monitor immediately
- evaluate the participant to determine, in consultation with the Lilly medical monitor, whether study intervention should be interrupted or whether the dose should be reduced
- closely monitor the participant for any AE/SAE and laboratory abnormalities until study intervention no longer has a clinical effect, and report the overdose event as an AE and document, and
- appropriate supportive treatment should be initiated according to the participant's clinical signs and symptoms.

6.8. Concomitant Therapy

6.8.1. Concomitant Therapy Regimens

Participants will be permitted to use concomitant medications that they require during the study, except certain medications that may interfere with the assessment of efficacy and safety characteristics of the study treatments.

Prohibited medications are listed in Section 6.8.3.

Permitted use of antihyperglycemic treatments other than study intervention is described in Section 6.8.4.

Reduction and/or discontinuation of concomitant antihyperglycemic treatments other than study intervention are described in Section 6.8.5.

Participants should consult with authorized study personnel before taking any new medications or supplements during the study. Authorized study personnel should consult the Lilly medical monitor if there are any questions about concomitant therapies during the study.

6.8.2. Concomitant Therapy Data Collection

Any medication or vaccine including over-the-counter or prescription medicines, vitamins, and/or herbal supplements that the participant is receiving at the time of enrollment or receives during the study, authorized study personnel should collect

- name of medication, vaccine, or therapy
- reason for use
- dates of administration, including start and end dates, and
- dosage information, including dose and frequency for concomitant therapy of special interest.

The Lilly medical monitor should be contacted if there are any questions regarding concomitant or prior therapy.

Non-study medications taken by participants who are screened but not randomly assigned to study intervention will not be reported to Lilly unless an SAE or AE occurs that the investigator believes may have been caused by a study procedure.

6.8.3. Prohibited Concomitant Medications

The medications prohibited in the study include medications intended to promote weight loss and non-study GLP-1 RA, DPP-4 inhibitors, and amylin mimetics. This includes prescribed or over-the-counter or alternative remedies. Examples include, but are not limited to

- pramlintide
- semaglutide
- sibutramine
- saxagliptin
- sitagliptin
- Contrave®
- orlistat
- Plenify®
- lorcaserin
- lixisenatide
- liraglutide
- alogliptin
- linagliptin
- zonisamide
- topiramate
- phentermine
- mazindol

6.8.4. Allowed Antihyperglycemic Treatments other than Study Interventions

Antihyperglycemic medications other than study interventions are ONLY allowed during these circumstances:

- for participants who require permanent discontinuation of study intervention but remain in the study
- for rescue therapy after randomization due to severe, persistent hyperglycemia, as described in Section 6.1.4
- during the safety follow-up period or ED visit, and
- short-term insulin use for up to 14 days is allowed for certain clinical situations, for example, elective surgery, during hospitalization, and hyperosmolar states, and must be differentiated from insulin use as rescue therapy when reported in the CRF.

6.8.5. Reduction and/or Discontinuation of Concomitant Antihyperglycemic Medications

Temporary discontinuation of concomitant antihyperglycemic medications <14 consecutive days is allowed for certain clinical situations, for example, severe dehydration, elective surgery, or need for radiologic examination involving IV iodinated contrast dye.

After randomization, discontinuation, dose modification, or formulation change of metformin, sulfonylurea, or SGLT-2i are not permitted except in the following situations:

- If a participant is on a sulfonylurea and develops hypoglycemia, defined as glucose <70 mg/dL, or is at risk of developing hypoglycemia, then the sulfonylurea dose can be reduced or discontinued.
- If a participant meets the criteria for severe, persistent hyperglycemia (Section 8.3.3.7) or discontinues study intervention, then the sulfonylurea dose may be increased according to country-specific label.
- In certain situations that require short-term discontinuation in line with the product(s) local labeling.
- In the event of multiple (>1) hypoglycemic episodes (glucose concentration <54 mg/dL or severe hypoglycemia), in participants on any oral treatment combination not including sulfonylurea, but on dual or single oral treatment of metformin and/or SGLT-2i, the dose of metformin or SGLT-2i can be reduced or discontinued.

7. Discontinuation of Study Intervention and Participant Discontinuation/Withdrawal

Discontinuation of specific sites or of the study as a whole are handled as part of Section [10.1.9](#).

7.1. Discontinuation of Study Intervention

When necessary, a participant may be permanently discontinued from study intervention. If so, the participant will remain in the study and follow procedures for the remaining study visits, as shown in the SoA (Section [1.3](#)).

A participant must be permanently discontinued from study intervention if

- the participant becomes pregnant during the study
- the participant is diagnosed with T1D or LADA
- the participant requests to discontinue intervention
- the participant develops confirmed pancreatitis (if not confirmed, study intervention may be restarted)
- the participant is diagnosed with MTC, C-cell hyperplasia, or MEN 2 after randomization or has calcitonin value ≥ 35 ng/L that has increased at least 50% over baseline after randomization
- the participant is diagnosed with an active malignancy or if a previously treated malignancy becomes known after randomization
- the participant experiences a significant study intervention-related hypersensitivity reaction after administration of study intervention
- any other AE, SAE, or clinically significant laboratory value for which the investigator believes that permanent study intervention discontinuation is the appropriate measure to be taken
- in the opinion of the investigator, the participant should permanently discontinue the study intervention for safety reasons
- if the participant, for any reason, requires treatment with a therapeutic agent that is prohibited by the protocol and has been demonstrated to be effective for treatment of the study indication. In this case, discontinuation from the study intervention occurs prior to introduction of the new agent.

Additionally, a participant should be permanently discontinued from dulaglutide according to the locally approved labeling and packaging.

7.1.1. Liver Chemistry Stopping Criteria

7.1.1.1. Interrupting Study Drug based on Elevated Liver Tests

The study drug should be **interrupted** and close hepatic monitoring initiated (see Section 8.2.7.1) if one or more of these conditions occur:

Elevation	Exception
ALT or AST >8x ULN	
ALT or AST >5x ULN for more than 2 weeks	
ALT or AST >3x ULN and either TBL >2x ULN or INR >1.5	For participants with Gilbert's syndrome: If baseline direct bilirubin is >0.5 mg/dL, then doubling of direct bilirubin should be used for drug interruption decisions rather than TBL >2x ULN.
ALT or AST >3x ULN with the appearance of fatigue, nausea, vomiting, right upper quadrant pain or tenderness, fever, rash, and/or eosinophilia (>5%)	
ALP >3x ULN, when the source of increased ALP is the liver	
ALP >2.5x ULN and TBL >2x ULN	For participants with Gilbert's syndrome: If baseline direct bilirubin is >0.5 mg/dL then doubling of direct bilirubin should be used for drug interruption decisions rather than TBL >2x ULN.
ALP >2.5x ULN with the appearance of fatigue, nausea, vomiting, right upper quadrant pain or tenderness, fever, rash, and/or eosinophilia (>5%)	

Source: FDA Guidance for Industry: Drug-Induced Liver Injury: Premarketing Clinical Evaluation, July 2009 and other consensus guidelines, with minor modifications.

Abbreviations: ALP = alkaline phosphatase; ALT = alanine aminotransferase; AST = aspartate aminotransferase; INR = international normalized ratio; TBL = total bilirubin level; ULN = upper limit of normal.

